3.14.2.7 Secondary Efficacy Endpoints Analysis

The additional secondary efficacy endpoint for the RWP is:

- ***A $\geq 20\%$ reduction from DEP baseline in blood Phe level at Week 4.***

The proportion of participants achieving a $\geq 20\%$ reduction in blood Phe level from baseline to Week 4 will be tested between the placebo and SYNB1934v1 treatment groups using a Fisher's Exact test.

This will be an observed-case analysis approach using the responder RWP FAS such that if a participant is missing the data needed to determine the endpoint, they will be considered as not having met the endpoint.

3.14.2.8 Exploratory Endpoints Analysis

The following are the analysis methods for the set of Exploratory endpoints.

For the dichotomous endpoints, this will be an observed-case analysis approach such that if a participant is missing the data needed to determine the endpoint, they will be considered as not having met the endpoint. For the continuous endpoint, this will be an observed-case analysis.

The following analyses will be performed on the responder RWP FAS

- ***Change from baseline to Week 1 in blood Phe level***

The analysis of the change from RWP baseline to Week 1 in blood Phe level will be a part of the RWP primary efficacy analysis, described in [Section 3.14.2.1](#) for responder RWP FAS.

- ***Percent change from baseline to Week 1, and Week 4 in blood Phe level***

The percent change from RWP baseline to Week 1, Week 3, and Week 4 in blood Phe level, will be analyzed using an MMRM analysis similar to the model described for the RWP primary efficacy analysis ([Section 3.14.2.1](#)), with the dependent variable being the percent change in blood Phe level from RWP baseline, and the RWP baseline blood Phe level as the baseline blood Phe level covariate.

- ***Blood Phe level $\leq 600 \mu\text{mol/L}$ at Week 4***

The proportion of participants meeting the Blood Phe level $\leq 600 \mu\text{mol/L}$ at Week 4 criteria, will be tested between the placebo and SYNB1934v1 treatment groups using a Fisher's Exact test.

The following analyses will be performed on the nonresponder RWP FAS.

- ***Change from baseline to Week 1 and Week 4 in blood Phe level***

The analysis of the change from RWP baseline to Weeks 1 and 4 in blood Phe level will be analyzed as described in [Section 3.14.2.1](#) using the nonresponder RWP FAS.

- ***Percent change from baseline to Week 1 and Week 4 in blood Phe level***

The percent change in blood Phe level from RWP baseline to Week 1 and from RWP baseline to Week 4, will be analyzed using an MMRM analysis similar to the model described for the RWP primary efficacy analysis ([Section 3.14.2.1](#)), with the dependent variable being the percent change in blood Phe level from RWP baseline, and the RWP baseline blood Phe level as the baseline blood Phe level covariate.

- ***Blood Phe level $\leq 360 \mu\text{mol/L}$ at Week 4***

The proportion of participants meeting the Blood Phe level $\leq 360 \mu\text{mol/L}$ at Week 4 criteria, will be tested between the placebo and SYNB1934v1 treatment groups using a Fisher's Exact test. The analysis will be repeated using a criterion of $\leq 360 \mu\text{mol/L}$.

- ***A ≥ 20% reduction from DEP baseline in blood Phe level at Week 4***

The proportion of participants achieving a $\geq 20\%$ reduction in blood Phe level from baseline to Week 4 will be tested between the placebo and SYNB1934v1 treatment groups using a Fisher's Exact test.

- ***Change from DEP baseline to Week 4 in blood Phe level***

The change from DEP baseline to Week 4 in blood Phe level, will be analyzed using an MMRM analysis similar to the model described for the RWP primary efficacy analysis ([Section 3.14.2.1](#)), with the dependent variable being the change in blood Phe level from DEP baseline, and the DEP baseline blood Phe level as the baseline blood Phe level covariate.

- ***Percent change from DEP baseline in blood Phe level at Week 4***

The percent change from DEP baseline to Week 4 in blood Phe level, will be analyzed using an MMRM analysis similar to the model described for the RWP primary efficacy analysis ([Section 3.14.2.1](#)), with the dependent variable being the percent change in blood Phe level from DEP baseline, and the DEP baseline blood Phe level as the baseline blood Phe level covariate.

3.14.2.9 Subgroup Analyses

The RWP primary and key secondary efficacy analyses will be performed for the following subgroups (as defined in [Section 3.5.1](#)):

- Participants on sapropterin dihydrochloride (Kuvan) at the DEP baseline visit
- Genotypic phenotype values (GPV) subgroups.

Additionally, if a dose was discontinued (see [Section 3.17](#)) the RWP primary and key secondary efficacy endpoint analyses will be performed on the subgroup of participants who had been excluded from the RWP FAS.

As a supplemental analysis, summary statistics for the following endpoints will be performed on the RWP FAS adolescent subgroup:

- Change and percent change from RWP baseline to Week 4.
- Change and percent change from DEP baseline to Week 4.
- Blood Phe Level $\leq 360 \mu\text{mol/L}$ at Week 4.

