### **5.5.3. Clinical Laboratory Measurements**

Clinical safety laboratory tests will be performed at the time points specified in [Table 5](#) and [Table 6](#): chemistry panel, CBC with differential, and creatinine clearance. A pregnancy test for WOCBP and an FSH test for postmenopausal women will be performed at the time points specified in the Schedule of Events. See [Appendix 1](#) for a list of clinical laboratory tests.

Screening results will be assessed by the investigator for inclusion of participants in the study. Additionally, unscheduled clinical laboratory tests may be obtained at any time during the study at the investigator's discretion. The diagnosis corresponding to any clinically significant abnormality or abnormality requiring treatment/intervention must be recorded as an AE.

If genetic testing for PAH mutations was performed before screening, these data may be submitted at the time of screening. Genetic testing is not required for entry into the study, and no sample will be drawn for DNA analysis.

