3.5.1 Subgroups

For selected efficacy and safety analyses (see [Section 3.14](#) and [Section 3.15](#), respectively) the summaries will be performed overall and by responder/nonresponder subgroups (i.e., as defined in [Section 3.5](#)).

The DEP will contain an optional substudy (DEP weekly substudy) to evaluate the range and variability of Phe and Tyr response at each dose level (see [Section 2.3.2](#)). The twenty participants in this substudy will have weekly Phe and Tyr value assessments during the DEP. The weekly Phe and Tyr assessments will be summarized for this subgroup.

The following additional subgroups will also be considered:

- Adolescents: Note that, for non-US sites, participants 12 to 17 years of age may be enrolled after the first 20 participants have completed the DEP, with approval of the DMC.
- Participants on sapropterin dihydrochloride (Kuvan) at the DEP baseline visit (i.e., DEP study day 1).
- Genotypic phenotype values (GPV) subgroups: For the subset of participants who have non-missing results for allele #1 and allele #2 (i.e., from the Genotyping eCRF page), their GPV will be calculated. The GPV will be calculated by entering the allele information into the following website <http://www.biopku.org/biopku/search-allele-start.asp>. The GPV is a number from 0 to 10; the following 3 subgroups will be considered based on the GPV score: 0-2.7, 2.8-6.6, 6.7-10.0.
- Participants in the DEP who had an iTD of a dose that was discontinued (i.e., this subgroup will only be utilized if a dose is discontinued as per the DMCs recommendation as defined in [Section 3.17](#)).
- Participants in the RWP who were excluded from the RWP FAS (i.e., this subgroup will only be utilized if a dose is discontinued as per the DMCs recommendation as defined in [Section 3.17](#)).

The analyses to be performed on these subgroups will be discussed in the corresponding efficacy and safety sections.

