3.14.1.9 Subgroup Analyses

The DEP primary and key secondary efficacy analyses will be performed for the following subgroups (as defined in [Section 3.5.1](#)):

- Participants on sapropterin dihydrochloride (Kuvan) at the DEP baseline visit
- Genotypic phenotype values (GPV) subgroups.

Additionally, if a dose was discontinued (see [Section 3.17](#)) the DEP primary and key secondary efficacy endpoint analyses will be performed on the subgroup of participants who had an iTD of a discontinued dose. For the DEP primary endpoint analysis, the MMRM analysis would be performed including the participants who had an iTD corresponding to a discontinued dose(s), in addition to the participants with an iTD corresponding to the retained doses.

As a supplemental analysis, summary statistics for the following endpoints will be performed on the DEP FAS adolescent subgroup:

- Change and percent change from baseline in blood Phe level at last measurement of the iTD of SYNB1934v1.
- A $\geq 20\%$ reduction from baseline in blood Phe level at any time in the DEP

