3.14.2.1 Primary Efficacy Endpoint Analysis

The RWP primary efficacy endpoint is the change from RWP baseline to Week 4 in blood Phe level. An MMRM analysis will be used to compare the mean change in blood Phe level between the placebo and SYNB1934v1 dose groups. The MMRM model will have treatment group, Screening Blood Phe (as a dichotomous variable: $\leq / > 720 \mu\text{mol/L}$), RWP baseline blood Phe level, iTD dose level, visit, and visit \times treatment group (interaction effect), visit \times iTD dose level (interaction effect), and visit \times RWP baseline blood Phe level (interaction effect) as fixed effects. The MMRM will also incorporate the participant's repeated measures at visits Weeks 1, 3, and 4, with visit being treated as a categorical variable. Least-squares means for both treatment groups and the SYNB1934v1 treatment group difference from placebo, along with the corresponding [REDACTED] confidence intervals and p-values will be calculated for Weeks 1, 3, and 4. The primary efficacy analysis will compare the least-squares means treatment difference between SYNB1934v1 and placebo in the change from baseline in the blood Phe level at Week 4.

At each of the scheduled assessments, blood Phe will be drawn in duplicate. The MMRM will incorporate these participant repeated measures. For the MMRM analysis, the results of each of the post-baseline duplicate samples from a visit will be included in the statistical model (i.e., without averaging the results within a given visit before inclusion into the MMRM).

The MMRM analysis will be based on the restricted maximum likelihood method. A Kenward-Roger approximation will be used for the denominator degrees of freedom. The covariance structure for the repeated-measures will be a direct product of unstructured (i.e., for the visits) and compound symmetry for the repeated assessments at a particular visit (i.e., the subject-level repeated measures has 2 dimensions, post-baseline Weeks 1, 3, and 4, as well as the 2 assessments at each visit. As such the covariance structure will use the direct product structure "UN@CS" as defined in SAS PROC Mixed).

For the dependent variable, this will be an observed-case analysis using the responder RWP FAS population, missing data will not be imputed.

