3.14.2.6 Control of Multiplicity

The overall Type I error rate for the RWP will also be controlled at the [REDACTED] for the primary endpoint (i.e., DEP, and RWP, will each have a 2-sided Type I error rate of [REDACTED]). The control of multiplicity at [REDACTED] within each study part is consistent with this study having 3 parts, with each study part having a distinct set of objectives, endpoints, and analysis populations.

For the RWP, the 3 key secondary endpoints will be tested at the [REDACTED] level using a fixed sequential testing methodology in this order:

- 1) Percent change from DEP baseline to Week 4 in blood Phe level.
- 2) Change from DEP baseline to Week 4 in blood Phe level
- 3) Blood Phe level $\leq 360 \mu\text{mol/mL}$ at Week 4

These key secondary endpoints will be tested following this prespecified order only if the RWP primary efficacy endpoint null hypothesis is rejected. An endpoint analysis will be considered statistically significant if the corresponding test for that analysis and all previous endpoint analyses are statistically significant using a [REDACTED] Type I error rate [REDACTED]

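### The RWP subgroup plan tests within sapropterin users and three GPV bands separately, so it cannot show whether the effect differs by subgroup

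*SAP*

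**What the plan says.** SAP 3.14.2.9 (RWP): "The RWP primary and key secondary efficacy analyses will be performed for the following subgroups". The list has two entries, sapropterin users and the GPV subgroups. SAP 3.14.1.9 does the same for Part 1: "The DEP primary and key secondary efficacy analyses will be performed for the following subgroups".

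The subgroups are defined in SAP 3.5.1. The sapropterin entry is users only: "Participants on sapropterin dihydrochloride (Kuvan) at the DEP baseline visit". For GPV, "the following 3 subgroups will be considered based on the GPV score: 0-2.7, 2.8-6.6, 6.7-10.0". GPV is calculated "For the subset of participants who have non-missing results for allele #1 and allele #2", and Protocol 5.5.3 adds: "Genetic testing is not required for entry into the study".

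The primary model to be repeated (SAP 3.14.2.1) yields least-squares means by arm and their difference; its "confidence intervals and p-values will be calculated for Weeks 1, 3, and 4". It has no subgroup term. The multiplicity section (SAP 3.14.2.6) covers the primary endpoint and then three key secondary endpoints: "These key secondary endpoints will be tested following this prespecified order only if the RWP primary efficacy endpoint null hypothesis is rejected". It does not mention subgroups.

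Neither subgroup section gives an interaction test, a non-user estimate, a minimum subgroup size or a rule for reading the results. Neither carries an exploratory label. In both sections the adolescent subgroup gets summary statistics only, described as supplemental.

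**The concern.** A subgroup analysis is normally meant to answer whether the treatment effect differs between kinds of participant. Separate tests inside each subgroup answer another question: whether this subgroup, at its own size, reaches p<0.05. Small subgroups often fail that test when the drug works equally well in everyone, and the tables then suggest an effect in one genotype class and none in another.

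For sapropterin the gap is wider, because users are analysed with nothing beside them. Protocol 1.6 argues that sapropterin users could benefit from the added drug and expects no interaction between the two agents. A users-only p-value cannot examine that expectation, and a non-significant one could be misread as no benefit on top of sapropterin.

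**Working it through.** **Inputs**
- RWP difference 245 µmol/L, SD of change 247 µmol/L, 1:1 allocation, two-sided alpha 0.05, power by t-test (Protocol synopsis, Sample Size Considerations).
- Three GPV bands plus sapropterin users, so four subgroups (SAP 3.5.1). With the primary and three key secondary endpoints, the RWP has 4 × 4 = 16 subgroup analyses.
- Assumptions, because the documents do not give them: overall RWP power of 80% to 98%, equal GPV thirds with every responder genotyped, and sapropterin users at 25% to 50% of responders. That last range is borrowed from the sapropterin-responsive share quoted in Protocol 1.2; it is not a figure for this trial.

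**The plan's own power figures.** The RWP size and power are redacted and cannot be reproduced. The one visible figure is over 98% for the DEP. With mean change 11% and SD 17%, a one-sample t-test reaches 98% at 41 evaluable participants, or 41/0.9 = 45.6, so 46 enrolled. That is plausible, but the DEP size is redacted too.

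**Step 1: RWP size.** Two-sample noncentral t with standardised effect 245/247 = 0.992. Reaching 80%, 90%, 95% and 98% power takes 17, 23, 28 and 34 evaluable responders per arm.

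**Step 2: one GPV third.** Use n/3 per arm, unrounded, in the same formula. Let p be the power in one band. With disjoint bands, all three are significant with probability p³, none with (1−p)³, and some but not all with 1 − p³ − (1−p)³.

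| Responders per arm | Per arm in a third | p | All three significant | None | Mixed |
|---|---|---|---|---|---|
| 17 | 5.7 | 0.32 | 0.03 | 0.31 | 0.66 |
| 23 | 7.7 | 0.44 | 0.08 | 0.18 | 0.74 |
| 28 | 9.3 | 0.52 | 0.14 | 0.11 | 0.75 |
| 34 | 11.3 | 0.61 | 0.23 | 0.06 | 0.71 |

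The true effect is identical in all bands in every row. Simulation of the same setting gives mixed patterns at about the same rates. A 2-degree-of-freedom treatment-by-GPV interaction F test on the same simulated data rejects in about 5% of trials.

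**Step 3: sapropterin users.** With subgroup sizes rounded to whole participants, power in users is 22% to 46% for an 80% design and 40% to 71% for a 95% design.

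**Step 4: inert drug, primary endpoint.** Four independent tests give 1 − 0.95⁴ = 18.5%. Simulation with an overlapping sapropterin group gives about 18%.

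**Step 5: fit of the model.** At one degree of freedom per term, the repeated model has: intercept 1, treatment 1, screening stratum 1, baseline 1, iTD 2, visit 2, visit × treatment 2, visit × iTD 4, visit × baseline 2, a total of 16 fixed-effect parameters. It also has the UN@CS covariance. A GPV third holds about 12 to 22 people, so the model may not fit. Since genotyping is optional, the bands may be smaller still.

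**The case against.** The strongest reply is that nothing in the trial's conclusions hangs on these subgroups. SAP 2.1 places the primary evidence of efficacy in the RWP comparison with placebo. SAP 3.14.2.6 fixes the confirmatory sequence, and no decision rule attaches to any subgroup. The subgroups and GPV cut-points are prespecified, and Protocol 1.6 reads more like an expectation of consistency than a planned subgroup claim. All of this stands, and it limits the point to interpretation.

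Three stronger readings are tempting but not supported:
- **The subgroup tests inflate the trial's type I error.** They do not. They lie outside the sequence and receive no confirmatory alpha.
- **With an inert drug, a false positive somewhere is more likely than not.** Independence over 16 tests gives 1 − 0.95¹⁶ = 56%, but the endpoints are correlated and one uses Fisher's exact test, whose true size is at most 0.6% with 6 per arm and 2.1% with 8. Allowing for both, simulation gives roughly 0.3 to 0.45 for between-endpoint correlations of 0.9 down to 0.3 (assuming 20% at or below 360 µmol/L and 40% sapropterin users). On the primary endpoint the figure is about 18%.
- **Sapropterin non-users are left out.** They are in every overall analysis, and sapropterin use is tabulated as yes or no at baseline (SAP 3.8). Only a separate estimate of their treatment effect is missing.

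The table shells are in a separate document, so labels or footnotes there cannot be ruled out. They would not supply the missing comparison.

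**Conclusion.** The concern holds as a weakness in what the subgroup results can support. As written, SAP 3.14.2.9 cannot show whether the effect differs by sapropterin use or GPV. If the planned effect is the same in all three GPV bands, at least one band is non-significant in about 77% to 97% of trials (1 − p³), and a spurious mixed pattern appears in about 66% to 75%, against about 5% false findings of a difference with an interaction test.

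These figures rest on an assumed 17 to 34 responders per arm, equal thirds, full genotyping and a simple t-test at Week 4. Incomplete genotyping would lower the power in each band; covariate adjustment could raise it. The overall primary conclusion is not at risk. Better reporting is available at little cost, so the change should be made before unblinding.

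**What to change.** **SAP 3.14.2.9.** For the RWP primary and the two continuous key secondary endpoints, fit the corresponding RWP model once per subgroup factor, adding subgroup, subgroup × visit, treatment × subgroup and treatment × subgroup × visit.
- Sapropterin: the responder RWP FAS, with users and non-users as the two levels.
- GPV: responder RWP FAS participants with both alleles recorded.
- Report the Week 4 treatment difference with its confidence interval for every level, and the Week 4 treatment-by-subgroup contrast as the interaction test.
- For Phe ≤360 µmol/L, report proportions by arm and the difference with an interval for each level.
- State that subgroup results are exploratory. State also that neither a within-subgroup p-value nor an interval that excludes or includes zero supports a claim of effect, or of no effect, in one subgroup. Removing p-values alone would not be enough, because a 95% interval carries the same test.

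**SAP 3.14.1.9.** The DEP has a single arm, so report estimates and intervals for users, non-users and each GPV band.

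**Cost.** SAP wording and modest reprogramming on data already collected; the confirmatory analysis does not change. The interaction test will have low power, so the estimates and intervals should lead, and no nominal p-value will be available for a favourable subgroup.

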3.14.3 Part 3: OLE

The following set of OLE endpoints will be performed separately for the responder and nonresponder OLE FAS. For the dichotomous endpoints, this will be an observed-case analysis approach such that if a participant is missing the data needed to determine the endpoint, they will be considered as not having met the endpoint. For the continuous endpoint, this will be an observed-case analysis.

- ***Change from DEP baseline in blood Phe levels***

At each scheduled OLE assessment timepoint, summary statistics for change from DEP will be provided.

Additionally, the change from DEP baseline in blood Phe levels will be analyzed using MMRM. The dependent variable is the change from DEP baseline in blood Phe level at each of the scheduled assessment timepoints in the OLE. Least-squares means for the change from baseline, along with the corresponding [REDACTED] intervals and p-values testing a change from baseline equal to 0, will be calculated.

Note that the least-squares means will use the observed margins approach (i.e., as opposed to equal weighting across the 3 iTD dose levels, the weighting will be proportional to the number non-missing percent change from baseline observations in each of the 3 iTD dose levels).

- ***Blood Phe level $\leq 360 \mu\text{mol/L}$***

At each scheduled OLE assessment timepoint, the number and proportion of participants meeting the corresponding criteria will be summarized along with [REDACTED] (i.e., [REDACTED]).

In addition to the analysis being performed on the responder/nonresponder OLE FAS populations, this analysis will be performed stratified on if a participant had a had an increase in 3-day dietary Phe (i.e. as discussed in [Section 3.10.2](#)) relative to DEP Baseline at each particular visit (i.e., at each timepoint summaries will be performed for the following groups:

- Responder OLE
- Nonresponder OLE
- Responder OLE participants who had an increase in 3-day dietary Phe*
- Responder OLE participants who did not have an increase in 3-day dietary Phe*
- Nonresponder OLE participants who had an increase in 3-day dietary Phe*
- Nonresponder OLE participants who did not have an increase in 3-day dietary Phe*

* Note: if a participant has a missing value for the 3-day dietary Phe at the OLE timepoint or at DEP baseline, the participant will be excluded from the analysis.

- ***Change from DEP baseline in blood Phe levels over time***

At each scheduled OLE assessment timepoint, summary statistics for change from DEP will be provided overall and stratified on the participants increase in dietary Phe (see [Section 3.10.2](#)) using the following categories:

- 0 mg/kg/day (i.e., no increase)
- 1-20 mg/kg/day
- 21-40 mg/kg/day
- >40 mg/kg/day.

- ***Change from DEP baseline in blood Phe level over time until first protocol-specified increase in dietary protein intake.***

At each scheduled OLE assessment timepoint, summary statistics for change from DEP in blood Phe level will be provided. This analysis will exclude observations which occur after the participant had their first protocol-specified increase in dietary protein.

- ***Change from DEP baseline in dietary Phe intake***

As discussed in [Section 3.10.2](#), at each scheduled OLE assessment timepoint, participants will have a 3-day dietary intake assessment. At each scheduled visit, the percent change from baseline in 3-day dietary Phe levels will be summarized.

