2.2 STUDY DESIGN

This is a 3-part, Phase 3 study consisting of a dose-escalating, open-label period (DEP; Part 1) of up to 15 weeks, followed by a 4-week, double-blind, placebo-controlled, randomized withdrawal period (RWP; Part 2), and an open-label extension (OLE; Part 3) of up to 36 months. [Figure 1](#) presents a study schematic.

In the DEP, all enrolled participants will maintain a stable diet reflecting their baseline Phe intake and receive escalating doses of SYNB1934v1 from approximately 3 to 15 weeks to determine an iTD, which is defined as the highest dose the participant is able to tolerate. A participant will be defined as having reached an iTD if they tolerate 3 weeks at a dose, regardless of whether other doses are tolerated.

Blood Phe level will be measured at each dose level after 3 weeks at that level. A responder will be defined as a participant who achieves a $\geq 20\%$ reduction in blood Phe level compared to DEP baseline on their iTD. For inclusion in the RWP primary efficacy analysis population, response will be assessed at the third week of a participant's established iTD for SYNB1934v1.

If at any time during a 3-week dosing interval in the DEP the participant or investigator considers a dose level to be intolerable, the dose may be de-escalated after discussion with the medical monitor. In this case, the participant will restart 3 weeks at the lower level iTD. After de-escalation, participants cannot escalate to a higher dose again during.

[figure not shown]
The DEP will contain an optional substudy (DEP weekly substudy) to evaluate the range and variability of [REDACTED] at each dose level. The [REDACTED] participants in this substudy will have weekly Phe and Tyr value assessments during the DEP (i.e., with Tyr assessments being primarily assessed for safety).

Once the first [REDACTED] participants have attained an iTD and completed the DEP or the [REDACTED] has a baseline DEP and has been in the study for [REDACTED], whichever occurs earlier, the DEP data will be evaluated by an independent Data Monitoring Committee (DMC). The DMC will use a pre-specified set of criteria based on both safety and efficacy to determine whether the dose regimen is appropriate or whether any doses should be discontinued as well as whether the study should be stopped for futility. Enrollment will not be paused during the interim analysis.

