2.3.1 Blood Phenylalanine and Tyrosine

Blood Phe and Tyr samples will be drawn 2.5 to 5 hours after the last meal. Phe and Tyr samples will be drawn in duplicate, using separate tubes from the same venipuncture, and analyzed separately. The time of the last meal will be recorded when taking Phe samples.

Baseline samples for DEP and RWP must be drawn prior to the first dose for those respective periods. During the DEP, blood Phe and Tyr will be measured at Week 3 of each completed dose level. During the OLE, blood Phe and Tyr will be measured quarterly. Blood Phe and Tyr will also be measured at early termination.

For all Tyr summaries the average value will be used, with the individual duplicate values being presented in the listings.

The individual duplicate blood Phe values will be used in some analyses, and the average of the duplicate values used for other analyses and summaries (see [Section 3.3](#)).

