3.3 Blood Phe Values at Baseline and Post-Baseline Visits

Baseline for blood Phe level in each of the 3 parts of the study will be defined as the mean of the duplicate blood Phe level measurements at the first visit of that part. If only one blood Phe level measurement is available, then that measure will be used as baseline. If the measurement at the first visit is missing, the most recent non-missing blood Phe levels from the central lab to the visit will be used (i.e., blood Phe levels from the local labs will not be used for analyses but can be used as for the inclusion criterion).

As defined in the schedule of events ([Table 11](#) and [Table 12](#)), the Part 2 RWP baseline is the End of the DEP visit, and the OLE baseline is the Part 2 RWP Week 4 visit.

Similarly, for the determination of responders and participants who achieve a specific reduction in Phe (e.g., Phe level $\leq 360 \mu\text{mol/L}$ at any time in the DEP, or a $\geq 20\%$ reduction from baseline), and in situations where a single-Phe value is needed for a particular visit (e.g., summary statistics over time), the mean of the duplicate blood Phe level measurements at the applicable post-baseline timepoint (e.g., Week 3) will be used. If only one of the duplicate blood Phe levels is available at a particular post-baseline timepoint, then that measurement will be used. Unless otherwise specified in the SAP, only the MMRM analyses of blood Phe will use the duplicate blood Phe assessments, all other summaries will use the average of the duplicate blood Phe measurements.

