3.4.3 Calculations for the DEP Responder

As discussed in [Section 2.2](#), a responder is defined as a participant who achieves a $\geq 20\%$ reduction in blood Phe level compared to DEP baseline. The following are additional details regarding the definition of a responder:

- A participant will be considered a responder if they met the $\geq 20\%$ reduction in blood Phe level at any time in the DEP.
- This will include the scheduled Week 3 blood Phe assessments at the end of each 3-week dosing period.
- This will not include assessments that were made specific to the participants included in the DEP Weekly substudy ([Section 2.3.2](#)).

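### The OLE analysis tests change from DEP baseline against 0 separately in responders and nonresponders, groups defined by change from that same baseline, so 0 is the wrong null value in both

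*SAP*

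**What the plan says.** SAP 3.14.3 opens with "The following set of OLE endpoints will be performed separately for the responder and nonresponder OLE FAS". For blood Phe it specifies an MMRM: "The dependent variable is the change from DEP baseline in blood Phe level at each of the scheduled assessment timepoints in the OLE". For the resulting least-squares means, "intervals and p-values testing a change from baseline equal to 0, will be calculated". The section names no comparator, gives no list of fixed effects, has no tested model for the two groups together, and carries no caution about how the groups were formed.

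Responder status comes from the DEP. SAP 3.4.3 counts a 20% or greater "reduction in blood Phe level at any time in the DEP", using the scheduled Week 3 visits. SAP 2.2 words the rule as a reduction "compared to DEP baseline on their iTD". The two rules differ and should be reconciled, but both measure the fall from DEP baseline.

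That baseline is one visit. SAP 3.3 says it "will be defined as the mean of the duplicate blood Phe level measurements at the first visit of that part", and SAP 2.3.1 has the duplicates drawn "using separate tubes from the same venipuncture". Averaging them reduces assay error but leaves day-to-day variation untouched. Protocol 1.6 supports the 20% threshold by comparing it with assay variability; neither document gives a within-person, visit-to-visit figure.

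SAP 2.1 places the primary evidence of efficacy in the RWP comparison. The multiplicity sections (SAP 3.14.1.6 and 3.14.2.6) cover the DEP and RWP only.

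**The concern.** One measured value does two jobs: it helps decide who is a responder, and it is the reference from which OLE change is calculated. Among people labelled responders, DEP baseline values that were too high by chance are over-represented. When Phe is measured again in the OLE it sits nearer the person's usual level, and the difference appears as a fall. Because the reference is fixed, this does not fade with time and can be mistaken for durability. Nonresponders are displaced the other way.

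In the RWP the randomised placebo group carries the same displacement, so it cancels in the comparison. Nothing in the OLE cancels it. At stake is the account of long-term efficacy in responders: an overstated mean change, with a p-value whose false-positive rate is far from nominal.

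**Working it through.** **1. The plan's own figures.** No power or error figure is stated for the OLE, and the enrolled N is redacted. The planning inputs in the protocol synopsis give a plausible trial size.

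- DEP: mean -11%, SD 17%, two-sided 0.05, power over 98%. A one-sample t-test with effect 11/17 = 0.647 has 97.9% power at n = 40 and 98.1% at n = 41. With 10% dropout, 41/0.90 = 45.6, so 46 enrolled.
- RWP: 245/247 = 0.992 needs 17 per arm for 80% power or 23 for 90%. With 5% RWP dropout, 50% responders and 10% DEP dropout: 34/0.95 → 36, /0.50 = 72, /0.90 = 80; or 46/0.95 → 49, /0.50 = 98, /0.90 → 109.

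The stated power is thus consistent with about 45 to 110 enrolled, but cannot be confirmed.

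**2. Mechanism.** Take an inert drug. On the log scale let baseline = μ + e0, a DEP visit = μ + e1 and an OLE visit = μ + e2, with independent errors of SD s. A responder has d = e1 − e0 ≤ ln 0.8 = −0.223. Since cov(e0, d) = −s² and var(d) = 2s², E[e0 | d] = −d/2. The expected OLE change is therefore E[e2 − e0 | responder] = E[d | d ≤ −0.223]/2, which is negative and the same at every OLE visit.

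**3. Worked value, one DEP visit, assumed CV 15%.** s = √ln(1 + 0.15²) = 0.149; SD of d = 0.149 × √2 = 0.211; z = −0.223/0.211 = −1.058. Chance responders: Φ(−1.058) = 14.5%. E[d | responder] = −0.211 × 0.228/0.145 = −0.331. Half is −0.166, a geometric mean change of about −15%. For nonresponders, 0.211 × 0.228/0.855/2 = 0.028, about +3%. Over everyone the expectation is 0.

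**4. Range of CV.** The documents give none, so 10-25% is assumed. As rough anchors, 17%/√2 = 12%, and 247/√2 = 175 µmol/L, or about 17-25% of 1000-700 µmol/L. Both planning SDs may also contain true differences in response.

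**5. Simulation, inert drug.** Further assumptions: median Phe 750 µmol/L, between-person log-SD 0.35, screening Phe > 360 µmol/L, 10% DEP dropout, 20% loss by the OLE. The test is a one-sample t-test in responders at one OLE visit, counting p < 0.05 in the direction of a fall (nominal: at most 2.5%).

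| Responder rule | CV | N = 46 | N = 80 | N = 109 | Stopped for futility |
|---|---|---|---|---|---|
| Any of 3 DEP visits (SAP 3.4.3) | 12% | 44% | 71% | 85% | about 60% |
| | 15% | 49% | 74% | 87% | about 23% |
| | 20% | 45% | 71% | 84% | about 5% |
| | 25% | 39% | 65% | 78% | about 1% |
| iTD visit only (SAP 2.2) | 12% | 28% | 41% | 57% | about 96% |
| | 15% | 31% | 52% | 67% | about 85% |
| | 20% | 33% | 60% | 74% | about 57% |
| | 25% | 36% | 63% | 75% | about 36-40% |

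The last column is the chance that fewer than 25% of the first 20 completers are responders. The rejection rates are over all simulated trials, stopped or not.

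With 45-100 completers, CV 10-25% and no loss before the OLE visit, the rates are roughly 45-95% with three DEP visits and 15-85% with one. Across settings the responder mean is about -105 to -190 µmol/L and the nonresponder mean about +7 to +125 µmol/L. Applied to all entrants together, the same test rejects in 3.7-6.3% of trials (two-sided), so the split by responder status causes the excess.

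**6. Several visits (any-time rule, CV 12-25%).** Averaged over four OLE visits, rejection is 60-70%, 88-94% and 96-98% at the three sizes. Significance at all four visits separately occurs in 9-15%, 29-42% and 48-63%.

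**The case against.** The strongest reply is that these p-values carry no confirmatory weight. That is correct, and it limits the point to description. A related argument is that if the RWP succeeds, a zero effect is already excluded and only the size is overstated. But the OLE question is whether the effect lasts. In a simulated drug with the planning effect of -11% in the DEP (assumed true between-person SD 5 points) and none in the OLE, 25 responders still showed -53 to -118 µmol/L, with p < 0.05 in 40-82% of trials.

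Second, the futility rule in SAP 3.17 would stop some inert-drug trials, mostly at low CV or with one DEP visit. It protects little at CV 15-25% under the any-time rule, and trials that pass it have a false-positive rate at least about as high.

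Third, participants below 240 µmol/L may modify their diet in the OLE, which could mask part of the apparent fall. SAP 3.14.3 has summaries by dietary change, but these do not address selection on baseline.

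Fourth, errors correlated between visits reduce the rate: 41-66% at N = 80 and CV 15-20%, for autocorrelation of 0.3-0.7 per step. That is still far above 2.5%.

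A reader might go further and infer that the responder p-value cannot fail, or that an inert drug would show a significant fall at every visit. The documents do not support either. Near-certain rejection appears if 25 responders are fixed in advance, but at CV 10% with one DEP visit only 5.7% of inert-drug participants are responders, so 25 would need about 25/0.057 ≈ 440 completers. Significance at all four visits is much less common than at one.

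**Conclusion.** Wrong as written. In SAP 3.14.3 the value 0 is not the correct null in either group, because group membership and the outcome share one DEP baseline visit and the OLE has no control. The direction of the bias follows from the definitions. Its size, and the rejection rates, rest on the assumed within-person CV, the number of DEP visits per participant, a redacted sample size and largely independent visit errors. A baseline covariate would not remove the bias.

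The consequence is confined to the description of long-term efficacy. It would be a mistake to infer that the RWP primary result is compromised: that comparison is randomised within responders, so both arms carry the same selection.

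**What to change.** In SAP 3.14.3, fit the MMRM with its interval and p-value on all OLE participants who came through the DEP/RWP, responders and nonresponders together, and label the result as uncontrolled. Show responder and nonresponder least-squares means descriptively, without p-values against 0, with a footnote that the groups were selected on change from the same baseline.

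The same edit should define the OLE FAS, which 3.14.3 uses but SAP 3.5 does not define, and state how anyone enrolled directly into the OLE is handled, since such participants have no DEP responder status.

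The cost is SAP wording and one pooled model in place of two tested ones; no visit, sample or data collection changes. Pooling removes the selection bias but not the other limits of an uncontrolled extension (diet change, re-titration, dropout), hence the label. The downside for the sponsor is that the reported long-term mean will be less favourable than the responder-only figure.
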